27. Data Sharing: *If you intend to share, release, or present any identifiable subject data from this study, explain where, when, and to whom the identifiable information will be shared, presented or released, and how this will be communicated to the subjects beforehand.*

N/A

SECTION H: CONFLICT OF INTEREST

28. Conflicts of Interest (COI): *Does the Investigator or any protocol personnel have an affiliation, arrangement, or financial interest that could be perceived as a conflict of interest? If yes, please describe.*

There are no Conflicts of Interest to report.

***Note:** All Covered Individuals in GMR research are required to have a current COI disclosure on file in Mentis (this must be complete prior to approval of the protocol). Covered Individuals are those with responsibilities for the conduct, design, or reporting of this research study.

SECTION I: REQUIRED ADDITIONAL ATTACHMENTS

29. Upload finalized versions of the following documents as applicable to your study in the electronic submission system:

- Survey instruments / questionnaires (and any versions translated into other languages)
- Demographics surveys
- Interview questions / prompts
- Focus group instructions / questions / prompts
- Observation data collection sheets
- Psychological & educational tests
- Educational materials
- All recruitment materials including flyers, ads, scripts, emails, social media posts, etc.
- Informed Consent Documents / cover letters and translated versions (See [Forms Page](#) for Templates)
- Permission letters from non-UTA study sites / collaborating organizations
- Signed Non-UTA Collaborator Forms & HSP Training ([Collaborative Research Page](#))

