If, after completion of this initial pre-screening interview, the subject meets study eligibility and is interested in enrolling, we will schedule a screening visit (see below for details). If enrolled, the PROMIS form will be coded with subject number. Pre-screening 'failures' will be tracked for date of contact and reason for ineligibility; however, if not enrolled, all pre-screening information is de-identified and destroyed.

Screening/Familiarization Visit (see attached document labeled "screening protocol"):

In the event that a subject does not meet the inclusion criteria following the screening visit, we suggest that the follow-up with a physician or mental healthcare provider (see attached document labeled "script study exclusion").

1. The participant signs the informed consent before screening procedures begin. After the participant signs the consent, we provide the participant a photocopy.
2. Participants complete a standard health history form (see attached document labeled "medical history form").
3. The investigator measures height (stadiometer), weight (digital scale), waist circumference (tape measure), blood pressure (mercury sphygmomanometer), heart rate (Welch Allyn Connex), and temperature (Welch Allyn SureTemp Plus).
4. Premenopausal women will provide a urine sample for a pregnancy test.
5. [name] or a trained investigator administers the Mini International Neuropsychiatric Interview (MINI) to determine depression status (see attached). The MINI has 16 sections and takes ~20 minutes to complete.
 - If a participant indicates an illness other depression, we give the participants a copy of the "Local Mental Health Providers" document (see attached document labeled "mental health providers"), strongly encourage them to follow-up with a clinician, and exclude the participant from the study.
 - If a participant indicates a "high" level of suicidality (coded as scoring ≥ 17 on the Suicidality Module) and immediate risk with intent to harm, MHMR Tarrant County Crisis Relief will be called for an external evaluation and study personnel will ensure the participant's safe transfer to MHMR personnel or facility.
6. Participants are familiarized with, and practice, the experimental measurements/procedures described in detail below.

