***Note: Additional forms may be required for your population. Obtain these from the [Forms & Templates Page](#).**

For Individuals with Impaired Decision Making Capacity: Upload [Form 2A](#).

For Pregnant Women, Fetuses, Women Undergoing In-Vitro Fertilization, or newborns: Upload [Form 2B](#).

For Prisoners (Individuals involuntarily detained): Upload [Form 2C](#).

For Children (Under 18 or the local legal adult age): Upload [Form 2D](#).

13. Inclusion Criteria: *List all criteria for including subjects, and explain the methods you will use to determine whether a subject is eligible based on your criteria (i.e. pre-screen, medical chart review). If your study is/will be funded, ensure that the inclusion criteria listed here match the details in your proposal.*

- Men and women 18 – 55 years,
- Two subject groups will be recruited:
 1. Healthy control (HC) subjects will not have a history of MDD or other major psychiatric illness; PROMIS score < 18; and as confirmed by MINI
 2. MDD patients will have clinically significant depression (non-medicated); PROMIS score > 18; and as confirmed by the MINI

14. Exclusion Criteria: *Explain any specific factors or contraindications that would make a subject ineligible to participate in this study, even if they would otherwise meet the inclusion criteria listed above. If your study is/will be funded, ensure that the exclusion criteria listed here match the details in your proposal.*

The exclusion criteria is applied to all groups. We will not enroll Non-English speaking individuals. This protocol involves the use of numerous questionnaires, including a detailed neuropsychiatric interview with the investigators. In addition, participants need to understand English in order to follow instructions and comply with procedures conducted during the screening and experimental visits.

Subjects will be excluded at the discretion of PI/collaborating psychiatrist/examining clinician or for any of the following reasons:

- Psychiatric illness aside from MDD (including bipolar disorder, panic disorder, schizophrenia)
- Psychiatric treatment with medication
- Active suicidal/homicidal ideation
- Active substance dependence
- Eating disorders
- Medications that could conceivably alter neurovascular function
- Changes or alterations in medication status (starting a new, additional, or different medication)
- Cardiovascular, renal, or metabolic disease (hypertension, heart disease, diabetes, hyperlipidemia)
- Tobacco use

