***Note:** You are responsible for maintaining accurate and confidential records regarding payment of your subjects. Per [Accounting Services procedures](#), compensation must be documented for tax purposes using a W-9 form unless an exception is granted by the Accounting department. Obtaining an exception should be considered for cases of sensitive research or when disclosure of a subject's identity would expose them to high risk. Exception requests are submitted through the [Business Affairs Exceptions Tracker \(BAET\)](#) in SharePoint. Refer to knowledge base article [KB0010632](#) for guidance. Contact Business Technology Services at [contact] or submit a ServiceNow ticket at <https://uta.service-now.com/selfservice/> for assistance.

17. Compensation: Describe any compensation to subjects for participation, including monetary payments, gift cards, course/extra credit, raffle prizes, goods or services, donations to charity, etc. Describe how and when you will provide the payment to the subjects, and how confidentiality will be maintained (for example, use of coding in payment log books/receipts). If you intend to hold a raffle, explain when you expect that the raffle will be drawn, and how participants will be contacted if they win the drawing. For course / extra credit, alternative non-research assignments must be offered for an equal amount of credit.

Participants will be compensated at the completion of the study or after the final visit to the lab.

For the screening visit, subjects will be compensated \$30. This compensation will only be provided to participants who qualify. That is, if the MINI or medical health history indicate an exclusion criterion and the subject is not enrolled in the study, he will not be compensated.

For the experimental visit, subjects are compensated \$75. Additional compensation is not provided if the participant is asked to repeat a trial within the same experimental visit. However, if a participant is asked to repeat the experimental visit, they will be compensated for the completion of the second visit as described above.

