Screening: The screening includes blood sample, height, waist circumference, weight, heart rate, blood pressure, pregnancy test, and history performed by the competent research staff. Participants may be uncomfortable giving medical information or being measured. The participants may decline to answer questions or participate in measurements. The researchers conduct screenings professionally and privately.

Latex: Some gloves and medical materials are made of latex rubber. Some people may be sensitive to latex. Screening identifies and excludes candidates having a known latex allergy.

Confidentiality: There is a risk of loss of confidentiality.

22. Strategies to Minimize Risks: *Explain the strategies that the research team will use to minimize the potential risks listed above.*

General Procedures

The research group's members are trained and competent in their duties. The group, led by [name], evaluates the effectiveness and safety of protocols and procedures in an ongoing fashion. They discuss the protocol with candidates, invite questions, and offer tours of the laboratory. Prior to medical screening, candidates read and sign informed consent forms detailing protocols, procedures, risks, sensations, compensation, etc. The researchers give candidates witnessed copies of the signed consent forms. After accepting participants into the study, the researchers discuss and review the procedures and protocols with them generally and at each step throughout the project. They frequently remind participants of the option to withdraw from the study at any time. Restricting access to experiments, data, and coding to authorized personnel maintains confidentiality. Lists of emergency numbers remain by lab telephones. At least one cell phone is present at each experiment. A hospital and emergency medical services are within 1-2 miles of the lab. An AED hangs nearby in the hallway.

The PI has obtained an IND number from the FDA for the pharmacological agents used with this protocol (IND 125,994). We are in complete compliance with FDA regulations. The agents are individually logged in a log book (quantity of agent, date of arrival and lot number). The date of use is then logged into the log book.

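### Paying the $30 screening fee only to those who qualify creates an avoidable incentive to misreport at the interview that confirms group status and screens for suicidality

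*Protocol*

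**What the plan says.** **Payment rule.** Protocol Section D, item 17 sets $30 for the screening visit and then limits it: "This compensation will only be provided to participants who qualify". It spells out the consequence: "if the MINI or medical health history indicate an exclusion criterion and the subject is not enrolled in the study, he will not be compensated". On timing it says: "Participants will be compensated at the completion of the study or after the final visit to the lab". Those who go on can earn $75 for the experimental visit and $15 for the daily stress survey, or $20 if all 8 days are completed. No section offers part payment to people who fail screening.

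**What happens at that visit.** Under Section B, item 6 (Screening/Familiarization Visit), the candidate signs consent, completes a health history form, and is interviewed by an investigator who "administers the Mini International Neuropsychiatric Interview (MINI) to determine depression status". An illness other than depression leads to exclusion. The same interview contains the Suicidality Module, whose score is part of the trigger for the crisis procedure. Section B, item 7 allows up to 2.5 hours for the visit.

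**What excludes.** Section C, item 13 bars a history of MDD in controls and requires the MINI to confirm both groups. Item 14 lists, among others, other psychiatric illness, psychiatric medication, tobacco use, eating disorders and "Active suicidal/homicidal ideation".

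**What candidates know beforehand.** Section F, item 22 says that before medical screening "candidates read and sign informed consent forms detailing protocols, procedures, risks, sensations, compensation, etc". Section E, item 19 has an investigator go through each section of the form with the participant.

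**The concern.** The health history and the MINI rest largely on what the candidate chooses to say. Under the payment rule, an answer that excludes also cancels pay for time already spent. That is a poor arrangement anywhere, and two features of this study make it worse.

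First, the MINI confirms the group variable. SAP section 4.3 enters MDD as a two-level predictor, and both aims rest on its interaction with the daily stress measure (β3). A control who hides a past depressive episode, or a participant who hides medication or tobacco use, would be analysed in a group whose definition they do not meet.

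Second, the interview is also where suicidality is first assessed. Active ideation is an exclusion, so the plan attaches a financial loss to a disclosure that its own safety procedure relies on.

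**Working it through.** The plan has no figure of its own to reproduce here. The check has four parts: what an excluding answer costs, which answers are affected, which of those are checked elsewhere, and what the fix would cost.

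**1. Cost of an excluding answer** (Section D, item 17; one survey period and one experimental visit)

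| Outcome of screening | Payment |
|---|---|
| Excluded on MINI or health history | $0 |
| Qualifies, completes, not all 8 survey days | 30 + 75 + 15 = $120 |
| Qualifies, completes, all 8 survey days | 30 + 75 + 20 = $125 |

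An excluding answer forfeits $30 for time already given, and access to a further 75 + 15 = $90 or 75 + 20 = $95. The first part exists only because of the rule in item 17. The second is pay for work not yet done. The $30 is 30/125 = 24% of the full completer payment.

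**2. Direction of the incentive**

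- *Would-be control with past MDD:* disclosure excludes, so the incentive is to under-report.
- *Either group, with another psychiatric illness, psychotropic medication, tobacco use, eating disorder or active suicidal ideation:* the incentive is again to under-report.
- *Candidate with current MDD and nothing else:* disclosure costs nothing, because MDD is a study group.
- *Candidate with a high PROMIS score who falls short of MDD on the MINI:* this person fits neither group in Section C, item 13, and the registration summary at the front of the Protocol excludes subthreshold depression. The incentive is to over-report.

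**3. What is asked or checked elsewhere**

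| Item | Other source in the Protocol |
|---|---|
| Medication, health history, tobacco | Asked at telephone or online pre-screening, also by self-report (Section B, item 6) |
| Current depressive symptoms | PROMIS at pre-screening; PHQ-9 at the experimental visit |
| Pregnancy, blood pressure, lipid and metabolic status | Urine test, measurement, blood panel |
| Suicidal or homicidal ideation with intent | Acted on at any time in the study (Section F, item 21) |
| Past MDD; other psychiatric history | No verification described beyond the MINI and health history |
| Concealed medication or tobacco use | Self-report only; no verification described |

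The last two rows are the exposed part.

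**4. Cost of paying everyone who attends**

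Cost = enrolled × failures per enrolled participant × $30. The documents give no screen-failure rate, so 0.5 to 1 failure per enrolled participant is an assumption.

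- 80 enrolled (SAP section 4.3): 80 × 0.5 × 30 = $1,200, to 80 × 1 × 30 = $2,400.
- 200 enrolled (maximum, Section C, item 15): 200 × 0.5 × 30 = $3,000, to 200 × 1 × 30 = $6,000.

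For comparison, full payment of 80 completers is 80 × 125 = $10,000.

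**The case against.** The strongest reply is that this is a choice about participant payment. It contradicts nothing in the plan, and its scientific consequence is conjecture. Several parts of that reply stand.

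- **No rate of concealment.** A reader might infer a definite loss of power for β3. The documents do not support one. Any such figure has to assume what share of controls is contaminated and that each carries the full MDD slope, and nothing ties either assumption to this $30. The planned sizes also differ in kind: 55 is for each predictor's partial correlation, 48 is for the interaction with negative affective reactivity, and 80 are to be tested. No power figure is therefore offered.
- **Existing checks.** It would be too broad to say that nothing is rechecked, as the third step of the working shows. A person who discloses medication or tobacco at pre-screening has given no visit time and loses no pay for it.
- **Delayed payment.** The $30 comes only at completion or after the last visit, so the pull is to qualify and continue, not to collect cash that day.
- **Safety.** A reader might infer that the rule will cause people at immediate risk to go undetected. The documents do not show that. The crisis call requires a high module score together with immediate risk and intent, later ideation is also acted on, and all participants receive mental-health resource and hotline information whatever they disclose.
- **Consent wording.** The consent form is not among the documents reviewed, so how clearly it states the condition cannot be checked. The Protocol says only that it details compensation and is reviewed section by section.

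The rule itself is not answered by any of this. It is explicit, it can be known in advance, nothing offsets it, and it bears on answers that the study cannot otherwise verify.

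**Conclusion.** The point holds as a cheap improvement to conduct. It is not an error in the statistical plan. Withholding $30 for a visit of up to 2.5 hours gives some candidates a reason to shade their answers at the interview that confirms group status and contains the Suicidality Module. The exposure is mainly past MDD in would-be controls, other psychiatric history, and concealed medication or tobacco use, with possible over-reporting by candidates just short of MDD.

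The link from payment to misreporting is an inference. It rests on the exclusions being largely self-reported and on the terms being known before screening. Its size cannot be computed from the documents. What can be stated is the money at stake: $30 for time already given, and $90 to $95 in later payments that depend on qualifying with or without a change.

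**What to change.** Amend Section D, item 17 so that everyone who attends the screening visit receives the screening payment, whatever the MINI, health history or other screening result, and put the same statement in the consent form. The timing sentence in item 17 also needs a clause saying when people who are not enrolled are paid, since payment is now tied to completion or the final visit.

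The cost is a minor IRB modification, revised consent wording and $30 per screen failure, in total the $1,200 to $2,400 (80 enrolled) or $3,000 to $6,000 (200 enrolled) worked out above under the assumed failure rate. No extra staff, procedures or eligibility changes are needed. The change removes the loss of pay for time already given. It does not remove the prospect of later payments, so it weakens the incentive without ending it.

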#### **4.3 Statistical Design and Power**

***Data Analytical Plan:*** Two psychosocial stressor exposure indicators will be calculated: stressor frequency (i.e., percentage of interview days during which at least one stressor occurred) and total stress (i.e., total number of stressors reported across all interview days). The emotion item ratings will be averaged to obtain daily negative affect scores, and scores will be aggregated for the 8 interview days. Negative affective reactivity will be defined as the magnitude of the change in negative affect on days when stressors occurred compared to negative affect on non-stressor days. Negative affective reactivity scores will be calculated using two-level multi-level modeling, as previously described. Muscle SNA will be quantified as burst occurrence (burst frequency) and size (burst area) and will be assessed during an overall baseline and in response to each laboratory-applied stressor. Beat-to-beat sympathetic transduction to the vasculature and to BP will be determined via spike-triggered averaging. Although daily stressor exposure and negative affective reactivity are the primary outcomes, exploratory analyses will expand our model of daily stress processes to examine the heterogeneity of the types of stressors experienced (stressor diversity) in relation to sympathetic reactivity in adults with MDD, which will provide additional insight to stress system dysfunction in depression and form the basis of subsequent proposals.

***Statistical Approach:*** To ensure robust and unbiased results, we will use defined protocols for classifying and testing subjects. For all aims, multiple experimental controls and orthogonal approaches are used, and relevant biological variables are factored into the research design and analyses. Data analysis will be blinded, when applicable, and performed by two independent investigators. Statistical significance will be accepted at  $p<0.05$ . Given our strict inclusion criteria, in order to achieve the required sample size of MDD patients, we will oversample young adults with MDD; healthy non-depressed adults will be recruited and matched on a 1:1 basis, such that an equivalent number of participants will be enrolled and tested in each group.

Multiple linear regression will be used to assess the relation between the primary outcome variable (sympathetic reactivity; continuous response variable) and two predictors: daily stressor processes (exposure and negative affective reactivity; continuous variables) and MDD (dichotomous between-group variable). The interaction between daily stressor processes and group will also be included in the model, such that:

$$\text{sympathetic reactivity} = \beta_0 + \beta_1 * \text{MDD} + \beta_2 * \text{daily stressor process} + \beta_3 * \text{MDD} * \text{daily stressor process} + e$$

In this model,  $\beta_0$  is the intercept,  $\beta_{1/2/3}$  are the regression coefficients for each variable (group, daily stressor process, and the interaction), and  $e$  is the random error, assumed to be normally distributed, with a mean of zero and constant variance. We hypothesize  $\beta_3$  will be significant such that the effect of daily stressor exposure (Aim 1) and negative affective reactivity (Aim 2) on sympathetic stress reactivity will be stronger in adults with MDD. All models will be tested with and without person mean stressor exposure to account for potential group differences in the frequency of daily stressor exposure. Sensitivity analyses will examine the effect of depressive symptom severity (continuous variable) instead of using the dichotomous MDD variable.

Sample size calculations are based on a power analysis for the squared semi-partial correlation between the response variable and each predictor that remains after controlling for the effect of the other predictor. Our preliminary data indicate the model  $R^2=0.40$ , with the two squared semi-partial correlation coefficients as 0.30 (stressor exposure) and 0.16 (group). Since a squared semi-partial correlation coefficient as low as 0.15 can be considered clinically relevant (medium effect size), a total sample size of 55 is a conservative estimate to detect a significant partial correlation between the response variable and each predictor after controlling for the effect of the other predictor (80% power at  $\alpha=0.05$ ; t-test). For negative affective reactivity, a sample size of 48 is a conservative estimate to detect a significant interaction effect (80% power at  $\alpha=0.05$ ; t-test). To account for attrition and potential experimental failure, we will test a total of 80 participants (40/group).

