To test our hypotheses, we will enroll healthy adults having no history of mood disorders and adults with major depressive disorder (MDD) having a broad range of depressive symptom severity. After screening, subjects will meet with the research coordinator or an investigator for a discussion, with opportunity for questions, before applicable consent forms are obtained. Daily stress processes will be assessed using an ecological momentary assessment approach for 8 consecutive days. On the last day of the daily stress assessment, we will directly measure muscle sympathetic nerve activity, blood pressure, and heart rate during acute laboratory-based cognitive, emotional, and physiological interventions to induce a stress response. A venous blood sample will be taken for measurements of metabolic and renal health and systemic inflammation.

Aim 1: To examine the effect of daily psychosocial stressor exposure on acute sympathetic stress reactivity in MDD. Two stressor exposure indicators will be calculated: stressor frequency (i.e., percentage of interview days during which at least one stressor occurred) and total stress (i.e., total number of stressors reported across all interview days) and will be related to the magnitude of responsiveness to the acute stress interventions. We hypothesize that the slope of this relation will be steeper in adults with MDD compared to healthy non-depressed adults.

Aim 2: To determine the relation between negative affective reactivity to daily psychosocial stressor exposure and acute sympathetic stress reactivity in MDD. Negative affective reactivity will be calculated as the change in affect on days when stressors occurred compared to one's typical affect on non-stressor days and will be related to the magnitude of responsiveness to the acute stress interventions. We hypothesize that the slope of this relation will be steeper in adults with MDD compared to healthy non-depressed adults.

Detailed Description:

Conditions

Conditions: Major Depressive Disorder

Keywords:

Study Design

Study Type: Interventional

Primary Purpose: Basic Science

Study Phase: N/A

Interventional Study Model: Single Group Assignment

Number of Arms: 1

Masking: None (Open Label)

Allocation: N/A

Enrollment: 100 [Anticipated]

Arms and Interventions

| Arms | Assigned Interventions |
|---|---|

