The proposed studies are complementary to those outlined in the PI’s funded NIH K99/R00 grant and, although not formally listed in the specific aims in the grant, these studies are described in the research strategy as alternative approaches to generate pilot data for future grant submissions.

Rationale:

Major Depressive Disorder (MDD) manifests in >15% of the population and is directly linked to the development of cardiovascular disease (CVD), independent of traditional cardiovascular risk factors. Importantly, CVD risk remains elevated even with the remission of depressive symptoms. Although multiple factors likely contribute, accumulating evidence indicates that vascular dysfunction plays a pathogenic role in depression-CVD comorbidity.

Exposure to psychological stress plays a critical role in the etiology of MDD and is itself associated with endothelial dysfunction, accelerated atherosclerosis progression, and increased CVD risk. Despite this clear epidemiological association, no studies have examined the relation between everyday psychosocial stressors and direct measures of neurovascular reactivity to acute stress in adults with MDD. Exposure to acute stressors includes activation of the autonomic nervous system, which can induce transient vascular dysfunction and exaggerated increases in blood pressure. Collectively, chronic and repetitive exposure to psychosocial stress, or a maladaptive response to repeated stressors (i.e., exaggerated stress reactivity), may accelerate the atherosclerotic process and precipitate the development of CVD.

In the laboratory, we propose to conduct a comprehensive examination of cardiovascular stress reactivity. We will then relate cardiovascular reactivity to daily psychosocial stressors in adults with MDD. Our central hypothesis is that adults with MDD will demonstrate altered sympathetic neural control of cardiovascular function and this impairment will be modulated by exposure to everyday psychosocial stressors; the resultant imbalance in vasodilator and vasoconstrictor regulation serves as a potential mechanistic link between daily stress and depression in increased CVD risk. Although the effects of daily stressors on activation of the hypothalamic-pituitary-adrenal axis are well-established, particularly in MDD, our proposed series of studies will test the novel concept that naturally-occurring daily stressors also directly influence sympathetic neural reactivity of the cardiovascular system.

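### Does leaving open absolute or percent change in muscle sympathetic activity undermine the group-by-stress interaction test (β3)?

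*SAP*

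**What the plan says.** SAP section 4.3, Data Analytical Plan, names two nerve-activity measures: "Muscle SNA will be quantified as burst occurrence (burst frequency) and size (burst area"). It adds that activity "will be assessed during an overall baseline and in response to each laboratory-applied stressor". The Statistical Approach makes sympathetic reactivity the continuous response in a linear regression on MDD, one daily stressor process and their product. The hypothesis on the product term, β3, is that the effect of daily stress "on sympathetic stress reactivity will be stronger in adults with MDD". The error term is "assumed to be normally distributed, with a mean of zero and constant variance".

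The registry text at the front of the Protocol states the same aim: "We hypothesize that the slope of this relation will be steeper in adults with MDD compared to healthy non-depressed adults". Its third primary outcome is a change in muscle sympathetic nerve activity relative to resting baseline activity. Protocol Section B, item 6 (Procedures), records five minutes of baseline before each laboratory task.

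None of this text gives a formula for the change score. The available SAP text begins at section 4.3, so an earlier definition cannot be ruled out.

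**The concern.** The predictors are each given a construction in section 4.3: stressor frequency, total stress and negative affective reactivity. The response is not. Absolute and percent change both fit the wording, and the regression has no term for resting activity.

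For a main effect this would be minor. An interaction is more sensitive, because dividing by the resting level rescales each group's slope. If resting levels differ, β3 on the absolute scale asks whether daily stress adds more nerve activity in MDD. On the percent scale it asks whether daily stress adds more relative to rest. Two careful analysts with the same recordings could then reach different verdicts on both aims. The safeguard in the SAP, "Data analysis will be blinded, when applicable, and performed by two independent investigators", does not settle a choice of formula unless both analysts work to the same rule.

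**Working it through.** **Inputs.** From SAP section 4.3: model R² 0.40; squared semi-partial correlations 0.30 (exposure) and 0.16 (group); 0.15 as the smallest relevant value; alpha 0.05 (two-sided assumed); 55 required; 80 tested, 40 per group. Assumed, because the documents give no resting values: the MDD-to-control ratio of resting activity, r.

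**1. The plan's own figure.** For one regression coefficient, the noncentrality is √(f²·N). With f² = 0.15, N = 55 and three predictors it is √8.25 = 2.87 on 51 degrees of freedom, and power is 80.5%. So 55 reproduces, and power at 80 is 92.8%. It reproduces with 0.15 entered as f². Read as a squared semi-partial with R² 0.40, f² = 0.15/0.60 = 0.25 and only 34 would be needed. The effect size is standardised, so the units of the change score do not enter the sample size.

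**2. How the scale enters β3.** Let s be the absolute slope and B the resting level, common within each group.
- Absolute β3 = s_MDD − s_HC
- Percent β3 = 100 × (s_MDD/B_MDD − s_HC/B_HC)

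For positive slopes, steeper in MDD on the percent scale requires s_MDD/s_HC > B_MDD/B_HC. Take a slope ratio of 1.5, so that absolute β3 is +50% of the control slope. As a share of the control percent slope, percent β3 is then:
- 1.5/1.25 − 1 = +20% at a resting ratio of 1.25
- 1.5/1.5 − 1 = 0 at 1.5
- 1.5/2.0 − 1 = −25% at 2.0

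At r = 1 the two scales agree.

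**3. How often the verdicts could part.** Set equal absolute slopes (absolute β3 = 0), residual variance 1 − 0.40 = 0.60, 40 per group, and no spread in resting level within a group. The table gives the percentage of 40,000 simulated studies in which β3 is significant on the percent scale.

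| Resting ratio r | 0.67 | 0.8 | 1.0 | 1.25 | 1.5 |
|---|---|---|---|---|---|
| Squared semi-partial 0.30 | 21.5 | 10.3 | 4.9 | 10.5 | 22.0 |
| Squared semi-partial 0.15 | 13.4 | 7.7 | 5.2 | 7.6 | 13.8 |

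Hand check for r = 1.5 and 0.30: noncentrality = 0.548 × (1/1.5 − 1) / (0.775 × √((1 + 1/2.25)/40)) = −1.24, which gives about 23%. If 0.15 is taken as f², as the plan's 55 implies, the last row falls to about 6.6% at 1.25 and about 10% at 1.5.

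**4. Is either scale unsound?** In a second simulation (80 participants, assumed resting SD of 3 bursts/min, mean of 5 stressors, 4,000 runs per setting), each scale was tested with its own null true and with the other scale's null true.

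| Assumed resting level, control / MDD (bursts/min) | Absolute null true: percent test rejects | Percent null true: absolute test rejects |
|---|---|---|
| 12 / 12 | 6.3% | 5.8% |
| 12 / 16 | 11.7% | 11.9% |
| 12 / 18 | 16.0% | 17.2% |
| 10 / 20 | 28.0% | 34.2% |

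When a scale's own null was true, its rejection rate stayed at 4.4% to 5.6%. The higher rates arise because, with unequal resting levels, a zero interaction on one scale is a non-zero interaction on the other. They are not excess false positives.

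**5. Constant variance.** Under the set-up of step 3, the MDD-to-control residual variance ratio on the percent scale is 1/r²: 1.56, 0.64 and 0.44 for r = 0.8, 1.25 and 1.5, and exactly 1 at r = 1. So the assumption fails on one scale only if resting levels differ. Even then the 1:1 design limits the harm. With 40 per group and equal spread V of the stressor measure, the pooled estimate of the variance of β3 is [(σ₁² + σ₂²)/2] × 2/(40V) = (σ₁² + σ₂²)/(40V), which is its true variance.

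**6. Baseline.** The analysis text names one reference, the overall baseline, and the registered outcome refers to resting baseline activity. The five-minute pre-task periods appear only in the task procedures; no analysis text makes them the reference.

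**The case for a change.** The strongest case for acting is that the algebra in step 2 needs no data, β3 carries both aims, and the model does not adjust for resting activity. A few sentences written before analysis would remove the doubt, at almost no cost. The Protocol's central hypothesis, in Section B, item 5, is that "adults with MDD will demonstrate altered sympathetic neural control of cardiovascular function", so equal resting activity should not be presumed. The SAP also does not expressly tie the change score to the overall baseline, or say whether burst frequency or burst area is the response for β3.

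Part of this stands. The formula is not in the available text, and neither the link to the overall baseline nor the choice of metric is spelled out. The inference from the central hypothesis does not stand. Altered control is not a claim about resting level, and the specific hypotheses that follow concern increases in sympathetic outflow and responses during acute stressors. Nor is there a better method on offer: percent change is unstable when resting activity is low, and absolute change ignores resting level. No effect has been quantified for the choice of baseline or of metric.

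**Conclusion.** The gap is real but is one of missing detail, and no change to the plan follows. Absolute and percent change are both conventional, and either one, followed as written, gives a sound test of a slope difference. The plan already names the baseline from which a competent analyst would work. The sample size does not depend on the choice.

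The possible consequence is conditional. At equal resting levels the two scales test the same null, apart from a small excess (6.3% and 5.8%) in the simulation with spread in resting level. At an assumed ratio of 1.25, a percent-scale test would find an interaction absent on the absolute scale in about 7% to 10% of studies. At 1.5 the figure is about 10% to 22%, depending on how the SAP's effect size is read. These figures rest on assumed resting ratios, on main-effect values from preliminary data whose outcome scale is not stated, and on exposure and group being uncorrelated. That last point is a simplification, since 0.30 + 0.16 = 0.46 exceeds the R² of 0.40. They show that two scales ask two questions when resting levels differ. They do not show that the planned analysis gives a wrong answer.
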